# 4 1. Introduction

21

Auditory verbal hallucinations (AVH) is a common symptom of schizophrenia . 5 Approximately 70-80% of schizophrenia patients have AVH at initial presentation , 6 of which 25%-30% are irresponsive to antipsychotic medication and persist . The 7 persistence of AVH can significantly diminish the quality of life and elevate the risks 8 of suicide and violence . Consequently, alternative therapies are urgently needed to 9 alleviate the severity and frequency of medication-resistant AVH. Repetitive 10 11 transcranial magnetic stimulation (rTMS) as a non-invasive therapeutic strategy offers a potential treatment for AVH in schizophrenia patients. An increasing number of 12 13 researchers place expectations on rTMS to ameliorate AVH, unfortunately, the efficacy of rTMS remains controversial . The conflicting clinical responses may be 14 attributed to the variability in rTMS sequences and target selections used across these 15 studies. 16 The selection of the rTMS sequence is key to achieving more robust clinical 17 efficacy. Although the efficacies in relieving AVH were mixed, a meta-analysis 18 19 reported that 1-Hz rTMS on temporo-parietal junction (TPJ) cortex was statistically superior to sham treatment 11, 12. The neuroimaging and neurophysiological studies 20

have indicated a correlation between AVH and heightened cerebral activity in the left

temporal cortex, suggesting that rTMS efficacy in alleviating AVH may be explained by its potential inhibitory effects . The continuous theta-burst stimulation (cTBS) paradigm has been proven to produce similar inhibitory effects on the motor system as 1-Hz rTMS . However, the stimulation period of typical cTBS (~ 40s) is much shorter than 1-Hz rTMS (~ 10min) for the same number of pulses, which is an advantage for clinical application. The cTBS paradigm has been applied in the treatment of many neurological and psychiatric disorders. Furthermore, biochemical analysis  and neuroimaging studies  have reported that a three-block TBS protocol (inter-block interval = 15 min) may induce cumulative aftereffects. Thus, we hypothesized that this multi-cTBS protocol would be effective in alleviating AVH in schizophrenia patients. Apart from the stimulation sequence, accurately identifying the stimulation target is crucial for enhancing clinical efficacy. Most studies investigating the potential of rTMS to alleviate AVH have chosen the TPJ cortex as a therapeutic target. Whereas, researchers typically rely on the T3P3 site of the international 10-20 system EEG electrode positioning to approximate the TPJ target. Considering the anatomical variability among patients, this approach proves imprecise in determining the exact TPJ target for each individual. In clinical rTMS studies, employing an image-guided navigation method can significantly enhance spatial precision, leading to more favorable outcomes . To address the clinical efficacy in treating AVH, we develop an optimized cTBS protocol that incorporates MRI navigation, an extended stimulation course (14 days), and a multi-block design (interval = 15 min). Our team

22

23

24

25

26

27

28

29

30

31

32

33

34

35

36

37

38

39

40

41

42

has discovered that the efficacy of optimized image-guided cTBS is significantly superior to both sham treatment and previous cTBS studies , as evidenced in an open-label trial . To mitigate the placebo effect, we are assessing the efficacy of this optimized cTBS protocol through a randomized, double-blind, placebo-controlled trial.

[figure not shown]
# 2. Objective

Based on the background mentioned above, we will investigate the clinical efficacy of the modified cTBS protocol through a randomized double-blind placebo-controlled trial. We hypothesize that this modified cTBS protocol would reduce AVH symptoms superior to sham controls.

# 3. Study Design

We will conduct a single-site, randomized, double-blinded, placebo-controlled clinical trial with two arms. The eligible patients with schizophrenia will be recruited through posted flyers and physician referrals from Anhui Mental Health Center (Hefei, China). In the screening phase, inclusion and exclusion criteria are investigated. Patients who meet the inclusion criteria will provide their written informed consent to participate and be randomly assigned to one of the groups to receive either active or sham cTBS treatment. Involved patients, clinical raters, and all personnel responsible for the clinical care of patients remain blinded to the allocated condition. Only rTMS administrators have access to the randomization list, but they have minimal contact with the patients and no role in assessing AVH. After the inclusion and randomization processes, patients will undergo three daily sessions of cTBS treatment for 2 weeks,

with assessments scheduled at three different visits: baseline (week 0), post-treatment (week 2), and a follow-up visit (week 6). Baseline assessments are conducted the day before the first cTBS session. Post-treatment and follow-up assessments are conducted one day and four weeks after the last cTBS session, respectively. The Auditory Hallucination Rating Scale (AHRS), the Positive and Negative Syndrome Scale (PANSS), the Hamilton Anxiety Rating Scale with 14 items (HAMA), and the Hamilton Depression Rating Scale with 17 items (HAMD) are assessed by a trained rater at baseline, post-treatment), and follow-up visit. These scales are applied to assess the severity of AVH and other symptoms. Furthermore, demographic data, structure magnetic resonance imaging (sMRI) and functional magnetic resonance imaging (fMRI) data are collected at baseline. The sMRI data will be used to navigate stimulation in real-time. The specific trial procedures are presented in Figure 1.

**Figure 1. Schematic representation of the trial procedures.** A, The trial consists of a 2-week rTMS treatment and three assessment visits at week 0, week 2, and week 6 (top). The clinical symptoms assessments include AHRS, PANSS, HAMA, and HAMD. B, The rTMS using continuous theta-burst stimulation (cTBS) paradigm will be performed with three daily sessions. The stimulation target on the

- 82 scalp will be navigated using Brainsight neuro-navigation software and individual structural MRI of
- 83 each participant. The specific target of temporo-parietal junction (TPJ) cortex and the schematic
- 84 diagram of the cTBS sequence as visualized at the bottom.
- 85 Abbreviations: MRI, magnetic resonance imaging; AHRS, Auditory Hallucination Rating Scale;
- 86 PANSS, Positive and Negative Syndrome Scale; HAMA, Hamilton Anxiety Rating Scale; HAMD,
- 87 Hamilton Depression Rating Scale; rTMS, repetitive transcranial magnetic stimulation.

#### 4. Inclusion and Exclusion Criteria

- Patients with the diagnosis of schizophrenia using the Structured Clinical Interview
- 90 for the Diagnostic and Statistical Manual of Mental Disorders, the 4th Edition will be
- 91 included, which will be applied by independent psychiatrists.
- 92 Here are some more detailed inclusion and exclusion criteria.
- 93 The inclusion criteria for patients included:
- 1) Aged 18 to 60 years old both genders;
- 2) patients with schizophrenia reported AVH at least 5 times per day using a written
- 96 log or hand-held counter;
- 97 3) the AVH symptoms of patients have failed to achieve a clinical response to
- 98 medication treatment (defined as an insufficient response to at least two antipsychotic
- agents, administered at adequate dosages for at least 6 weeks);
- 4) a stable dosage of antipsychotic medication for 2 weeks before inclusion and
- 101 keep the dose stable for the duration of the study.
- 102 Exclusion criteria included:

- 103 1) Focal brain lesions on T1- or T2-weighted fluid-attenuated inversion-recovery
- 104 MRI;

112

113

114

115

116

117

118

119

120

121

122

123

- 105 2) accompanied by other mental illness or history other than depression;
- 106 3) a history of severe head trauma or neurological disease;
- 4) recent aggression or other forms of behavioral dyscontrol;
- 5) a history of rTMS or electroconvulsive therapy;
- 6) with severe suicidal thoughts or behavior;
- 7) metal objects in the head or any other contraindication to MRI;
- 111 8) pregnant and current alcohol or drug abuse.

## 5. Randomization and Blinding

Patients will be randomly assigned to receive either active or sham cTBS treatments according to a computer-generated list by an unblinded investigator not involved with study ratings/analysis. The assignment will be executed by utilizing sealed opaque envelopes, each containing the code corresponding to the assigned group for every participant. To ensure the integrity of the double-blind procedure, patients, clinical raters, and all personnel responsible for the clinical care of patients will remain uninformed about the assigned condition until the end point of the study. Only rTMS administrators have access to the randomization list. For the sham cTBS group, we will use a sham coil with an appearance identical to the real coil, The only difference was that the sham coil generated only sound and sensations on the scalp similar to the real coil but no current, which prevents patients from identifying their

allocation to the rTMS group.

124

125

126

127

128

129

130

131

132

133

134

135

136

137

138

139

140

141

142

143

144

To measure blinding integrity, participants will be asked to guess which group they were randomly assigned to at the study endpoint. Participants are notified of the treatment condition at the endpoint. Participants in the placebo group will be given the opportunity to receive active treatment.

### 6. Interventions

Following randomization and baseline assessment, patients will undergo neuronavigated cTBS treatment. The cTBS will be performed using a MagStim Rapid transcranial magnetic stimulator (Magstim Company Ltd.) with a 70-mm air-cooled figure-of-eight coil. The frameless neuro-navigation system (Brainsight; Rogue Research, Montreal, OC, Canada) will be employed to position the coil for maximal field strength at the stimulation target regions for each participant. According to previous studies, the left TPJ may be an effective target for AVH in schizophrenia patients . Therefore, we restrict the stimulation target within the left TPJ, defined as a sphere of 6-mm radius centered at Montreal Neurological Institute (MNI) coordinates [-51, -31, 23] . This target is transformed into each participant's T1 space by applying an inverse matrix produced during T1 segmentation in SPM12 (www.fil.ion.ucl.ac.uk/spm) and an in-house TMStarget software . Then, each individual's target is imported into the neuro-navigation system. The junction points of the figure-of-eight coil will be placed directly over the TPJ region. The entire stimulation process will be monitored by real-time MRI

navigation.

145

146

147

148

149

150

151

152

153

154

155

156

157

158

159

160

161

162

163

164

165

166

Before the first treatment, each participant's resting motor threshold (RMT) will be determined according to a 5-step procedure over the primary motor cortex . RMT was defined as the lowest intensity required to evoke a small response (>50 mV) in more than five of ten consecutive trials in the right first dorsal interosseous muscle. Participants will then undergo 3 daily sessions of cTBS treatment for 2 weeks. One session was 40 seconds in duration and consisted of triplet 50-Hz bursts, repeated at 5 Hz until a total of 600 pulses was reached 16. To achieve cumulative aftereffects, this protocol was repeated 3 times (1,800 pulses in total) separated by two 15-minute breaks (controlled by a stopwatch) in line with previous methodological studies . During the 15-minute treatment interval, all patients were silent and rested with their eyes closed. The cTBS was delivered at 80% of the resting motor threshold (RMT)  or the highest intensity the stimulator could deliver for this protocol (50% of maximum output). Sham cTBS treatments will be delivered with the same rTMS protocol using a sham coil (Magstim Company Ltd.), identical in appearance to the real one. The only difference is that the sham coil generates only sound and sensations on the scalp similar to the real coil but no current, which prevents patients from identifying group allocation. Any adverse event related to the study (e.g., headache, pain, discomfort, or other harm caused by the intervention) will be recorded throughout the study. If serious

adverse events occur, the participant will immediately be withdrawn from the study.

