# 7.2 Secondary Outcomes

Secondary outcomes measures will include: 1) the changes from baseline to post-treatment and follow-up in the PANSS, HAMA and HAMD score; 2) the number of responders at post-treatment and follow-up (responder is defined as  $\geq$ 25% reduction from baseline in AHRS and PANSS total scores); 3) the adverse events and blinding integrity.

The flow chart for each patient is shown below (Table 1).

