### 178 **Table 1.** Schedule of Events

|                     | Screening and     | Post-treatment visit | Follow-up visit |
|---------------------|-------------------|----------------------|-----------------|
| Assessments         | baseline (Week 0) | (Week 2)             | (Week 6)        |
| Inclusion/exclusion | ×                 |                      |                 |
| criteria            | *                 |                      |                 |
| Informed consent    | ×                 |                      |                 |
| Randomization       | ×                 |                      |                 |
| Demographic data    | ×                 |                      |                 |
| MRI scan            | ×                 | ×                    |                 |
| RMT                 | ×                 |                      |                 |
| AHRS                | ×                 | ×                    | ×               |
| PANSS               | ×                 | ×                    | ×               |

| HAMA                     | × | × | × |
|--------------------------|---|---|---|
| HAMD                     | × | × | × |
| Adverse events record    |   | × | × |
| Blind integrity evaluate |   |   | × |

Abbreviations: MRI, magnetic resonance imaging; RMT, resting motor threshold; AHRS, Auditory Hallucination Rating Scale; PANSS, Positive and Negative Syndrome Scale; SAPS, Scale for Assessment of Positive Symptoms; SANS, the Scale for Assessment of Negative Symptoms; HAMA, Hamilton Anxiety Rating Scale; HAMD, Hamilton Depression Rating Scale.

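### Section 6 records only adverse events related to the study, although section 7.2 makes adverse events an outcome without that limit

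*Protocol*

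**What the plan says.** The only instruction on collecting adverse events is in section 6 (Interventions). It covers "Any adverse event related to the study (e.g., headache, pain, discomfort, or other harm caused by the intervention"), and the same sentence has recording run for the whole study. The section does not say who decides that an event is related, or how. Its next sentence, on serious adverse events, carries no condition about relatedness.

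Section 7.2 gives "the adverse events and blinding integrity" as the third group of secondary outcomes, without restricting it to related events.

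In Table 1 the row "Adverse events record" is marked at week 2 and week 6. Section 3 describes the trial "with assessments scheduled at three different visits: baseline (week 0), post-treatment" (week 2) and follow-up (week 6), so these are the only two assessment visits after treatment starts.

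On blinding, section 5 states: "Only rTMS administrators have access to the randomization list". Patients, clinical raters and the staff responsible for clinical care stay blinded.

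**The concern.** In a randomised sham-controlled trial, the effect of the stimulation on harms is read from the difference between arms in all events. Nobody has to decide the cause of a single event, because randomisation does that work for the groups. If cause is judged case by case before recording, part of the randomised comparison is replaced by opinion.

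The risk is practical in this population. Participants have medication-resistant hallucinations, so an episode of agitation or worsening is easily put down to the illness. If the stimulation contributed to it, the event is lost from the arm where it matters. What is at stake is whether the safety statement at the end of the trial can rest on the randomised comparison.

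**Working it through.** The plan gives no figure for this point, so there is none to reproduce. The check is a comparison of the sections, followed by a short argument in symbols.

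**1. What is collected (section 6).** Recording applies to study-related events. The examples after the general term illustrate it and do not define its limit, but all of them concern harm from the intervention, which points to a causal reading. No other sentence provides for recording events thought unrelated.

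**2. What is to be reported (section 7.2).** Adverse events, with no qualifier.

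**3. Side by side.** The outcome in section 7.2 is the full set, and the collection rule in section 6 yields a subset. The outcome as named cannot be built from the data as collected. This is a matter of collection, so it cannot be left to the analysis plan.

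**4. What a filter does to the difference between arms.** Use these symbols, none of which has a value in the protocol:

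- *b*: background events per participant, equal in both arms by randomisation
- *t*: extra events per participant on active compared with sham
- *u_A*, *u_S*: share of background events that is recorded on active and on sham
- *v*: share of the extra events that is recorded

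True difference = (*b* + *t*) − *b* = *t*.

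Recorded difference = (*b·u_A* + *t·v*) − *b·u_S* = *t·v* + *b*(*u_A* − *u_S*).

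Three cases follow:

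- If the filter removes only background events, and equally in both arms (*v* = 1, *u_A* = *u_S*), the recorded difference is *t*. Nothing is lost from the absolute difference.
- If some events caused by the stimulation are judged unrelated (*v* < 1, *u_A* = *u_S*), the recorded difference shrinks to *t·v*.
- If the judgement differs by arm (*u_A* ≠ *u_S*), the second term is added and can have either sign.

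If all events are recorded, *v* = *u_A* = *u_S* = 1, and the recorded difference is *t* without any assumption about how well cause was judged.

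**5. Result.** Under the wording of section 6, an unbiased comparison depends on the quality of an unassigned judgement. The protocol gives no event rates and no recording shares, so the bias has no computable size and its direction is not fixed.

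**The case against.** Four points can be made for the plan.

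*Timing.* From Table 1 a reader might infer that events are collected only at weeks 2 and 6, so that brief effects of a session depend on recall. The documents do not support this. The sentence in section 6 itself provides for recording over the whole study. Table 1 has columns for weeks 0, 2 and 6 only, so it has no place to show a treatment day. Its two marks fall on the only assessment visits after treatment starts and are compatible with continuous recording reviewed at those visits. At most, the table does not display what the text promises.

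*Who filters.* A reader might also infer that the unblinded stimulation administrators decide relatedness. The protocol does not say so. It names nobody for this task, and section 3 gives the administrators little contact with patients and no part in rating hallucinations. What stands is that the judgement is unassigned.

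*Other routes into the data.* It would go too far to say that events thought unrelated are lost altogether. AHRS, PANSS, HAMA and HAMD are scored at all three visits by a blinded rater, so psychotic or mood worsening present at a visit is measured whatever its cause. The sentence on serious events has no relatedness limit. These routes cover part of the gap: worsening that resolves between visits, and non-serious events outside these scales, have no other place to be recorded.

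*Wording.* Section 6 refers to the study, which is wider than the intervention, and section 7.2 has no limit. A generous site could therefore record everything. That is possible, but section 6 does not require it, and a case report form written from it could properly leave such events out.

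**Conclusion.** The point holds as a conflict between the collection rule in section 6 and the outcome in section 7.2. A judgement of relatedness, by an unnamed person, stands before the randomised safety comparison, and events attributed to the illness or other causes may go unrecorded.

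The size cannot be stated. Any percentage would rest wholly on assumed event rates and assumed recording shares, and the first case in the working shows that a filter need not change the absolute difference at all. The finding is that the comparison is left unprotected; it is not evidence that harm will be hidden.

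The conclusion assumes that staff follow section 6 as written and that no other trial document, such as a case report form instruction, widens it. The consequence is confined to a secondary safety outcome. The primary AHRS comparison is not affected. The change is still worth making before data collection, since unrecorded events cannot be restored later.

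**What to change.** 1. In section 6, replace the condition with an instruction to record all adverse events in both arms, from the first session to week 6, regardless of presumed cause.
2. Have relatedness rated as a separate item by a blinded clinician already on the study, and name that role.
3. Report all events and related events by arm. The layout of the tables can sit in the analysis plan.
4. As a clarification only, add a note under Table 1 that recording is continuous and is reviewed at weeks 2 and 6.

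The cost is a change of wording in section 6 and on the case report form, one extra rating per event, and a longer listing of mostly minor events. It needs no additional staff or visits and changes nothing in treatment or withdrawal.

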### 7. Measurement of Outcomes

# 7.1 Primary Outcome

167

168

171

172

173

174

175

176

The primary outcome is the changes in AHRS scores from baseline to posttreatment as well as follow-up.

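### After a serious adverse event, Section 6 withdraws the participant from the whole study rather than only from stimulation, so outcome and safety data are lost

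*Protocol*

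**What the plan says.** The last sentence of Section 6 (Interventions) sets the rule: after a serious adverse event, "the participant will immediately be withdrawn from the study". The sentence before it says that adverse events "will be recorded throughout the study".

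The data at stake are set out elsewhere in the protocol:

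- Section 7.1 defines the primary outcome as the "changes in AHRS scores from baseline to posttreatment as well as follow-up", so both post-baseline visits belong to it.
- Section 7.2 lists PANSS, HAMA and HAMD changes, response, and "the adverse events and blinding integrity" as secondary outcomes.
- Table 1 schedules the four scales at weeks 0, 2 and 6, the row "Adverse events record" at weeks 2 and 6, and the blinding assessment at week 6 only.
- Section 3 times the visits from the end of stimulation: "Post-treatment and follow-up assessments are conducted one day and four weeks after the last cTBS session".

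Section 8 allows for 10% attrition and Section 10 plans multiple imputation. Neither says that a participant who stops stimulation early is still assessed.

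**The concern.** Stopping treatment and leaving a trial are different decisions. A serious event can justify ending stimulation at once, but it gives no reason to stop observing the patient. The rule joins the two, with three consequences.

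- Whether AHRS is observed comes to depend on an event that the assigned treatment may have caused. Multiple imputation usually assumes data are missing at random, and that is doubtful for patients removed because of a serious event.
- From week 2 to week 6, which is 4 of the 6 study weeks, no stimulation remains. Withdrawal then spares the patient no exposure and only removes data.
- Adverse events are recorded for as long as the participant is in the study. The patients with the worst safety experience would therefore get the least trial safety follow-up, although adverse events are a listed outcome.

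This cannot be left to the statistical analysis plan. The rule decides which data are collected, and an analysis plan cannot recover ratings that were never taken.

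**Working it through.** **Is there a retaining provision?** Sections 3, 6, 7, 8 and 10 and Table 1 were read together. Section 3 and Table 1 schedule visits for participants in general. Section 8 budgets for loss and Section 10 imputes it. None keeps a withdrawn participant under assessment, follows the event to resolution, or adds an early-termination visit.

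**Ratings lost per participant (Table 1).**

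- Event during the course: 4 scales × 2 visits = 8 ratings, including both post-baseline AHRS ratings, plus the blinding guess.
- Event after week 2: 4 scales × 1 visit = 4 ratings, plus the blinding guess. The week-2 AHRS is kept.
- In both cases the triggering event itself is recorded, but its later course and any new events are not.

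**The plan's own sample size.** Inputs from Section 8 are effect size 0.76, power 80%, two-sided 5%, 30 per group, 10% attrition and 66 in total. A two-sample t-test needs 28.2 per arm, so 29; the normal approximation gives 28. The stated 30 is close to both. With attrition, 60 × 1.10 = 66, as stated, or 33 per arm.

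**Possible bias.** The protocol gives no serious-event rate, so this is an assumed scenario: k = 1 excess withdrawal in one arm of 33, with a true AHRS outcome worse than imputed by δ = 0.5 to 1 SD.

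- Shift in the group difference = (k/33) × δ.
- δ = 0.5: 0.5/33 = 0.015 SD; 0.015/0.76 = 2.0% of the planned effect.
- δ = 1: 1/33 = 0.030 SD; 0.030/0.76 = 4.0%.
- Standard error of the standardised difference = √(2/33) = 0.246, so the shift is 0.06 to 0.12 SE.

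Under these assumptions the shift favours the arm with the excess event. It is zero if events are balanced across arms with the same δ.

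**Power** (two-sample t-test, d = 0.76, two-sided 5%):

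| Observed | Power |
|---|---|
| 66 (33 v 33) | 86.0% |
| 65 (33 v 32) | 85.5% |
| 60 (30 v 30) | 82.5% |

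This is a single-timepoint approximation, not the planned mixed model.

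**Visit dates if early stoppers are kept.** Assume sessions on days 1 to 14 and apply Section 3's timing from the last session.

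- Last session on day 14: 14 + 1 = day 15 and 14 + 28 = day 42.
- Last session on day 4: 4 + 1 = day 5 and 4 + 28 = day 32, both 10 days early.

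A repair that keeps these patients must therefore also fix their visit dates.

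**The case against.** The strongest reply is that the sentence closes the section on interventions and follows one about harms from the intervention, so it may be meant only as a rule for stopping treatment. That is possible. The text nevertheless says study, and site staff follow what is written. If the narrower meaning was intended, the correction simply states it.

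The second reply is that the numerical effect is negligible: at most 0.12 SE in an assumed scenario, about half a percentage point of power, and still 82.5% power if all six attrition places are used. This stands as a description of the efficacy impact. But the attrition allowance and multiple imputation accept the loss without preventing it, and neither restores safety follow-up.

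Third, the text does not forbid clinical follow-up, and the consent pages, which are not in the reviewed text, might carry withdrawal terms. The finding is limited to the protocol as shown.

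Fourth, a serious event may lead to a medication change, despite the stable-dose requirement in inclusion criterion 4, and later ratings would then mix two effects. That affects how the ratings are analysed and interpreted. It is no reason not to collect them.

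Two smaller points are fair. The visit-timing conflict arises only once early stoppers are retained, so it bears on the remedy and is not a separate error. Section 6 describes recording "Any adverse event related to the study" but puts no such limit on the withdrawal rule; whether unrelated serious events are covered is a missing detail and is not pressed here.

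**Conclusion.** The concern holds. The protocol prescribes study withdrawal after a serious adverse event, and no provision shown keeps the later assessments. The certain cost is 8 scale ratings per participant withdrawn during the course, or 4 after week 2, together with the blinding guess and further safety recording.

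The effect on the treatment estimate is probably small: 0.015 to 0.030 SD for one excess event in one arm. That figure rests on an assumed event count and an assumed departure from the imputed values, since the protocol gives no event rate. Few patients are likely to be affected. The change is worth making mainly for safety follow-up and for keeping randomised patients observed, at very little cost.

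**What to change.** Replace the last sentence of Section 6 with wording such as:

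> If a serious adverse event occurs, stimulation is stopped immediately. Unless consent is withdrawn, the participant remains in the study and is assessed at calendar weeks 2 and 6, counted from the start of treatment and not from the last session received. The event is followed until it resolves or stabilises.

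Add a matching clause to the visit timing in Section 3, so that a participant who stops early is not rated on dates counted from the last session received.

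The cost is one sentence and one clause, plus modest effort to retain a few patients. Patient protection is unchanged, because stimulation still stops at once. If medication is changed after the event, the change should be recorded with the retained ratings so that the analysis can take it into account.
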